#### **4.5.5 Tumor and Response Evaluations**

Screening assessments must include CT scans (with oral/IV contrast unless contraindicated) or MRI of the chest, abdomen, and pelvis. A spiral CT scan of the chest may be obtained, but is not a requirement.

A CT (with contrast if not contraindicated) or MRI scan of the brain is required for patients with known CNS metastases, or to confirm or refute a diagnosis of CNS metastases at baseline in the event of symptoms or suspicion of CNS metastases. Patients with active CNS metastases are eligible for this study if non-symptomatic, treated and stable (please refer to Inclusion Criterion 11). If a CT scan for tumor assessment is performed in a positron emission tomography (PET)/CT scanner, the CT acquisition must be consistent with the standards for a full-contrast diagnostic CT scan.

Bone scans (Technetium-99m [TC-99m]) or sodium fluoride PET (NaF-PET) should be performed at screening if clinically indicated. If bone metastases are present at screening and cannot be seen on CT or MRI scans, or if clinically indicated, TC-99m or NaF-PET bone scans should be repeated when complete response is identified in target disease or when progression in bone is suspected.

CT scans of the neck or extremities should also be performed if clinically indicated and followed throughout the study if there is evidence of disease at screening. At the investigator's discretion, other methods of assessment of measurable disease as per RECIST v1.1 may be used.

Results of standard of care tests or examinations performed prior to obtaining Informed Consent and  $\leq$  28 days prior to study entry may be used for the purposes of Screening rather than repeating such tests.

For subsequent tumor assessments, procedures for tumor assessment should be performed as clinically indicated. The same radiographic procedure used to assess disease sites at screening should be used throughout the study (e.g., the same contrast protocol for CT scans). All known sites of disease must be documented at screening and reassessed at each subsequent tumor evaluation. Response will be assessed by the investigator using RECIST v1.1 and modified RECIST (see [Appendix 2](#) and [Appendix 3](#)). The same evaluator should perform assessments if possible to ensure internal consistency across visits.

At the investigator's discretion, CT scans should be repeated at any time if progressive disease is suspected.

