**Appendix 3**  
**Response Evaluation Criteria in Solid Tumors:**  
**Excerpt from Original Publication (cont.)**

**Table 3 Best Overall Response When Confirmation Is Required**

Overall Response at First Timepoint	Overall Response at Subsequent Timepoint	Best Overall Response
CR	CR	CR
CR	PR	SD, PD, or PR a
CR	SD	SD, provided minimum duration for SD was met; otherwise, PD
CR	PD	SD, provided minimum duration for SD was met; otherwise, PD
CR	NE	SD, provided minimum duration for SD was met; otherwise, NE
PR	CR	PR
PR	PR	PR
PR	SD	SD
PR	PD	SD, provided minimum duration for SD was met; otherwise, PD
PR	NE	SD, provided minimum duration for SD was met; otherwise, NE
NE	NE	NE

CR=complete response; NE=not evaluable; PD=progressive disease; PR=partial response; SD=stable disease.

a If a CR is truly met at the first timepoint, any disease seen at a subsequent timepoint, even disease meeting PR criteria relative to baseline, qualifies as PD at that point (since disease must have reappeared after CR). Best response would depend on whether the minimum duration for SD was met. However, sometimes CR may be claimed when subsequent scans suggest small lesions were likely still present and in fact the patient had PR, not CR, at the first timepoint. Under these circumstances, the original CR should be changed to PR and the best response is PR.

NOTE: In this study, stable disease must persist for at least 4 weeks (minimum duration) to be considered a bona fide SD.

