4.4.2.3 Overall Response

Overall response is determined separately on disease status using RECIST v1.1 and modified RECIST, both evaluated by the investigator.

Best overall response will be derived differently for RECIST assessments and for modified RECIST assessments.

Best overall response based on RECIST v1.1 assessments:

The assessment of best overall response includes post-screening RECIST assessments obtained up to

- disease progression

- death from any cause
- last evaluable RECIST assessment in the absence of disease progression or death
- start of a subsequent anti-cancer therapy

whatever occurs first.

A patient with complete response followed by complete response determined on two consecutive investigator assessments (≥ 4 weeks apart) has confirmed complete response as Best Overall Response.

Otherwise, a patient with complete response followed by partial response or partial response followed by complete response or partial response followed by partial response determined on two consecutive investigator assessments (≥ 4 weeks apart) has confirmed partial response as Best Overall Response.

Otherwise, if there exists at least an assessment of CR, PR or SD, then the patient has Stable disease as Best Overall Response.

If the patient has confirmed complete or partial response, the patient is an overall responder, otherwise, the patient is an overall non-responder. Therefore, if best overall response is Stable Disease, Progressive Disease, Non-Evaluable disease or missing, the patient is an overall non-responder.

Patients who never received treatment are considered as non-responder.

Best overall response based on modified RECIST assessments:

The assessment of best overall response includes post-screening RECIST assessments obtained up to

- death from any cause
- last evaluable RECIST assessment in the absence of death
- start of a subsequent anti-cancer therapy

whatever occurs first.

For best overall response based on modified RECIST, all RECIST assessments are considered even after progression.

The calculations of best overall response based on modified RECIST assessments is similar to the best overall response based on RECIST v1.1 assessments.

In case there are more than one occurrence of CR (or PR in the absence of CR), the first occurrence of CR (respectively PR) will be considered.

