4.4.2.5 Disease Control

Disease control is determined separately on disease status using RECIST v1.1 and modified RECIST, both evaluated by the investigator.

Disease control rate (DCR) is defined as the sum of the CR, PR and stable disease (SD) rates.

A patient with complete response followed by complete response determined on two consecutive investigator assessments (≥ 4 weeks apart) has confirmed complete response as Best Overall Response.

Otherwise, a patient with complete response followed by partial response or partial response followed by complete response or partial response followed by partial response determined on two consecutive investigator assessments (≥ 4 weeks apart) has confirmed partial response as Best Overall Response.

Otherwise, if there exists at least an assessment of CR, PR or SD, then the patient has Stable disease as Best Overall Response.

Patients who never received treatment are considered as non-responder.

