Age-adjusted Charlson comorbidity index	x				
12-lead ECG ^c	x		as clinically indicated		
Tumor sample	x ^d (mandatory)		Cycle 2, Day 1 (optional) ^e		
Weight	x		x	x	
Height	x				
Complete physical examination ^f	x			x	
Limited physical examination ^f			x ^g		
ECOG Performance Status	x		x ^g	x	
Vital signs ^h	x		x	x	
HIV, HBV, HCV serology ⁱ	x		as clinically indicated		
Hematology ^j		x	x ^g	x	
Coagulation (aPTT, INR)		x		x	
TSH, free T3, free T4			Every other cycle		
Serum chemistry ^k		x	x ^g	x	

	Screening Period ^a		Treatment Period	Treatment Discontinuation	Follow-Up Period
	Day -28 to Day -1	Day -14 to -1	Day 1 (± 3 days) of each 3 week treatment cycle	30 (± 7) days from last treatment or at initiation of other anti-cancer therapy (whichever occurs first)	
Urinalysis ^l		X	X ^g	X	
Pregnancy test ^m		X	X		
Tumor assessment ⁿ	X		Every 9 weeks ± 3 business days for 54 weeks from study treatment start; thereafter every 12 weeks ± 6 business days until confirmed PD or until study discontinuation (for patients who continue to receive atezolizumab following disease "pseudo-progression")		
EORTC QLQ-C30			Day 1 of first 3 cycles then with tumor assessments	X	
EQ-5D-5L			Day 1 of first 3 cycles then with tumor assessments	X	
Concomitant medications ^o	X		X	X	
Adverse events ^p	X		X	X	X
Study drug infusion			X		
Survival and anti-cancer therapy ^q				X	X

Abbreviations: aPTT: activated partial thromboplastin time; ECG: electrocardiogram; ECOG: Eastern Cooperative Oncology Group; EORTC: European Organisation for Research and Treatment of Cancer; INR: international normalized ratio; PD: progressive disease.

Note: Unless otherwise indicated, assessments scheduled on the study treatment days should be performed prior to initiation of study treatment infusion.

- a. Written informed consent is required for performing any study-specific tests or procedures. Results of standard-of-care tests or examinations performed prior to obtaining informed consent and within 28 days prior to study entry (except where otherwise specified) may be used for screening assessments rather than repeating such tests.
- b. Medical history includes surgical and cancer histories. Cancer history includes stage, date of diagnosis, and prior anti-cancer treatment. Reproductive status and smoking history should also be captured. Demographic information includes age, sex, and self-reported race/ethnicity.

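### SAP 4.4.2.3 and 4.4.2.5 omit the 4-week minimum for stable disease set in Protocol Appendix 3, and score CR then PR as confirmed PR without its note a (minor)

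*SAP*

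**What the plan says.** SAP 4.4.2.3 derives best overall response (BOR) in order. Two consecutive CRs at least 4 weeks apart make a confirmed CR. Next comes confirmed PR: "Otherwise, a patient with complete response followed by partial response or partial response followed by complete response or partial response followed by partial response", again consecutive and at least 4 weeks apart. Then comes stable disease: "Otherwise, if there exists at least an assessment of CR, PR or SD, then the patient has Stable disease as Best Overall Response". SAP 4.4.2.5 carries the same rule into DCR: "if there exists at least an assessment of CR, PR or SD, then the patient has Stable disease". No time condition is attached to SD in either section. For RECIST v1.1, the SAP uses assessments only up to progression, death or a new anti-cancer therapy.

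Protocol Appendix 3, Table 3, closes with a study-specific note: "In this study, stable disease must persist for at least 4 weeks (minimum duration) to be considered a bona fide SD". Five rows depend on that minimum. CR-SD, CR-PD and PR-PD give SD if it was met and PD if not. CR-NE and PR-NE give SD if it was met and NE if not. PR-SD gives SD unconditionally. CR-PR has three possible outcomes: SD, PD or PR. Under note a, if the CR was real, "any disease seen at a subsequent timepoint, even disease meeting PR criteria relative to baseline, qualifies as PD at that point". If the CR was claimed while small lesions were probably still present, "Under these circumstances, the original CR should be changed to PR and the best response is PR".

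The Schedule of Assessments (SAP Appendix 2, same as Protocol Appendix 1) sets scans "Every 9 weeks ± 3 business days for 54 weeks from study treatment start". Protocol 4.5.5 adds that, at the investigator's discretion, "CT scans should be repeated at any time if progressive disease is suspected".

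**The concern.** The SAP is what will be programmed, and it drops a condition that the protocol states for this study, without giving a reason. Take a patient with an SD reading on an unscheduled scan in week 3 who then progresses. The SAP counts that patient as disease controlled. Appendix 3 does not: the patient is PD, or NE if nothing evaluable follows. Early unscheduled scans are prompted by suspected progression, so they would tend to come from the patients whom a minimum duration is meant to screen out.

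The protocol does not say when the 4 weeks start, so two programmers could apply it differently.

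A second departure concerns CR followed by PR. The SAP always takes the PR branch and has no step that separates a miscalled CR from a real CR with relapse. A patient placed in the wrong branch counts as a responder in the overall response rate (ORR) and also enters the duration of response (DoR) analysis under SAP 4.4.2.4.

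DCR and ORR are secondary endpoints, and SAP 4.4.5 repeats them across many subgroups, some of which may be small.

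**Working it through.** The plan gives no figure for DCR or ORR that could be reproduced. The check compares the two rules case by case and then asks when they can differ under the scan schedule.

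**Step 1. Compare the rules.** Inputs are the SAP 4.4.2.3 hierarchy (pairs at least 4 weeks apart) and Appendix 3 Table 3 with note a and the 4-week note.

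| First, next reading | SAP | Appendix 3, minimum met | Appendix 3, minimum not met |
|---|---|---|---|
| CR, CR | CR | CR | CR |
| CR, PR (CR miscalled) | PR | PR | PR |
| CR, PR (CR genuine) | PR | SD | PD |
| CR, SD | SD | SD | PD |
| CR, PD | SD | SD | PD |
| CR, NE | SD | SD | NE |
| PR, CR and PR, PR | PR | PR | PR |
| PR, SD | SD | SD | SD |
| PR, PD | SD | SD | PD |
| PR, NE | SD | SD | NE |
| NE, NE | NE | NE | NE |
| SD, PD* | SD | SD | PD |
| SD, NE* | SD | SD | NE |

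*Not rows of Table 3; scored from the 4-week note.

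- When the minimum is met, DCR is identical in every row. ORR differs in one row only, genuine CR then PR.
- When it is not met, the SAP counts one more patient as disease controlled in eight rows: genuine CR-PR, CR-SD, CR-PD, CR-NE, PR-PD, PR-NE, SD-PD and SD-NE.
- SAP minus Appendix 3 is 0 or +1 patient in every row, never negative.

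**Step 2. When can the minimum be missed?** The first scheduled scan is at 9 weeks = 63 days. Three business days span at most 5 calendar days (assumption: one weekend). Earliest scheduled scan: 63 − 5 = day 58, which is more than 28. Counted from first dose, every scheduled reading meets the minimum. DCR can therefore differ only for a patient whose CR, PR or SD readings all come from unscheduled scans before day 28.

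**Step 3. Other origin.** If the 4 weeks ran from the first SD reading, scheduled scans would still be at least 63 − 2 × 5 = 53 days apart. Only an early unscheduled scan, or no later scan, could leave the minimum unmet. CR-NE and PR-NE can give SD although nothing evaluable follows the first reading, so Table 3 does not require a second non-PD scan.

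**Step 4. Size.** With N about 1000 (SAP 2.3), k affected patients shift a rate by k/1000.

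- DCR: k is unknown. For an assumed 0 to 30 patients the shift is 0.0 to 3.0 percentage points.
- ORR: for an assumed 0 to 20 genuine CR-then-PR patients the shift is 0.0 to 2.0 points. From an assumed 150/1000 = 15.0% (Clopper-Pearson 95% CI 12.8 to 17.4), 20 more responders give 170/1000 = 17.0% (14.7 to 19.5).
- In a subgroup of an assumed 20 patients, one reclassified patient is 1/20 = 5 points.

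These counts are illustrations; the documents contain none.

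**The case against.** The best defence is that Protocol 6.5 supports the SAP. It defines response as CR or PR on two consecutive assessments at least 4 weeks apart, which a CR-PR pair satisfies, and it defines DCR as a BOR of CR, PR or SD with no duration attached. On CR-PR this has weight: part of the tension lies inside the protocol. On SD it does not. Section 6.5 takes BOR as given, and the protocol points to Appendix 3 for RECIST v1.1, where the minimum is stated for this study.

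The second defence is that note a is largely applied before the data reach the SAP. An investigator who follows RECIST v1.1 records relapse after a real CR as PD, and the SAP stops at progression, so no CR-PR pair arises. The pairs that remain should mostly be miscalled CRs, where both documents give PR. This stands, and it limits the ORR effect to recording errors.

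The third defence is the schedule: scheduled scans cannot breach the minimum if it runs from first dose. This also stands.

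Three stronger conclusions that a reader might draw are not supported:

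- That Appendix 3 forbids PR after CR. PR is one of its three listed outcomes.
- That DCR and ORR must be overstated. These rules cannot lower either rate, but the effect can be zero. Another difference can pull ORR the other way: Protocol 6.5 ties response to measurable disease at baseline, while SAP 4.4.2.3 states no such restriction, and patients with only non-measurable disease can reach CR but not PR.
- That every patient with a single SD scan is misclassified. The rows ending in PD or NE give SD without a second non-PD scan.

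**Conclusion.** The SD rule in SAP 4.4.2.3 and 4.4.2.5 contradicts the 4-week minimum in Appendix 3. The error is one-directional for DCR but narrow, and probably close to zero. That rests on counting from first dose, which the protocol does not state but which matches the origin used for OS and PFS, and on scans following the schedule. The CR-then-PR rule is a lesser gap that matters only where PR was recorded after a genuine CR.

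The conflict is clearest for RECIST v1.1. For modified RECIST, Appendix 2 defines SD with no minimum of its own. One enters only through its default to RECIST v1.1 conventions, and the SAP says only that the modified derivation is similar.

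The point is minor: the endpoints are secondary and the study is descriptive, with no formal hypothesis. It is still worth correcting, because the rule is explicit and the change is cheap.

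**What to change.** 1. In SAP 4.4.2.3 and 4.4.2.5, assign RECIST v1.1 SD only when the 4-week minimum is met, and state that it is counted from first dose. Otherwise assign PD or NE by the matching Table 3 row. PR-SD stays SD.
2. Query every CR-then-PR sequence under RECIST v1.1. Under note a, either the first CR is recoded to PR or the second assessment is recoded to PD. Then derive BOR, ORR, DCR and DoR from the resolved data.
3. State whether the SD minimum also applies to modified RECIST.

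The cost is a few sentences, a small programming change and some site queries. DCR or ORR may fall slightly.

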### **3.3.7 Rationale for the Use of Modified Response Criteria (Immune Based)**

Cancer immunotherapies may result in early apparent radiographic progression (pseudoprogression/tumor immune infiltration), including the appearance of new lesions, followed by delayed response ([Wolchok et al. 2009](#)). Additionally, responding tumors may appear to increase in size because of the influx of immune cells ([Hoos et al. 2010](#); [Pennock et al. 2012](#)). Unconventional response patterns have been described in patients treated with anti-cytotoxic T lymphocyte-associated antigen 4 ([Wolchok et al. 2009](#)) and have been observed in the preliminary experience with atezolizumab in Study PCD4989g. Therefore, modified RECIST will be used in this study to accommodate the possible appearance of new lesions and to allow the apparent increase in tumor burden to be confirmed at a subsequent assessment prior to designation of progressive disease.

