### BEST OVERALL RESPONSE: ALL TIMEPOINTS

The best overall response is determined once all the data for the patient are known.

The best overall response according to modified RECIST is interpreted as below:

- **CR:** Complete disappearance of all tumor lesions (target and nontarget) and no new measurable or unmeasurable lesions, confirmed by a consecutive assessment  $\geq 4$  weeks from the date first documented. All lymph nodes short axes must be <10 mm.
- **PR:** Decrease in the sum of the diameters of all target and all new measurable lesions  $\geq 30\%$  relative to baseline, in the absence of CR, confirmed by a consecutive assessment  $\geq 4$  weeks from the date first documented.
- **SD:** Criteria for CR, PR, and PD are not met.

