## **Appendix 2**

### **Modified Response Evaluation Criteria in Solid Tumors (cont.)**

- **PD:** Increase in the sum of the diameters of all target and all new measurable lesions  $\geq 20\%$  relative to the nadir, which may be confirmed by a consecutive assessment  $\geq 4$  weeks from the date first documented as follows:

The confirmatory assessment shows an additional measurable increase in tumor burden as measured by the sum of the diameters of all target and all new measurable lesions.

This protocol allows patients to continue to receive study treatment even after confirmed radiographic PD per modified RECIST, and patients may achieve a best overall response of PR or CR based on tumor regression achieved at any time prior to study treatment discontinuation.

## Appendix 3

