4.4.2.2 Progression-Free Survival

Progression-free survival (PFS) is determined separately on disease status using RECIST v1.1 and modified RECIST, both evaluated by the investigator.

The date of disease progression is derived based on scan/assessment or death dates, not on visit dates. RECIST assessments/scans contributing towards a particular visit may be performed on different dates.

Progression-Free Survival based per RECIST v1.1 assessments:

PFS is defined as date of first occurrence of tumor progression (earliest of the dates of the RECIST component indicating tumor progression) or date of death (in the absence of tumor progression) by any cause or date of censoring, whichever occurs first, minus date of start of study treatment + 1.

For patients not known to have had a tumor progression or died, the date of censoring is the latest date of assessment from their last evaluable RECIST assessment or the date of start of subsequent cancer therapy whichever occurs first. Patients who never received treatment are censored with time equal to 1 day.

If a patient has no evaluable post-screening RECIST assessments, the patient is censored at the day of study treatment initiation unless the patient dies within 18 weeks. In the latter case, the death date will be used as the date of disease progression.

Progression-Free Survival based per modified RECIST assessments:

PFS according to modified RECIST is defined as:

- date of first occurrence of tumor progression after a modified confirmed response if the patient is a responder according to modified RECIST or
- date of first occurrence of tumor progression in case the patient is not a responder according to modified RECIST or
- date of death (in the absence of tumor progression) by any cause or
- date of censoring, whichever occurs first, minus date of start of study treatment + 1.

For patients not known to have had a tumor progression or died after that modified response, the date of censoring is the latest date of assessment from their last evaluable RECIST assessment or the date of start of subsequent cancer therapy whichever occurs first. Patients who never received treatment are censored with time equal to 1 day.

If a patient has no evaluable post-screening RECIST assessments, the patient is censored with time equal to 1 day unless the patient dies within 18 weeks. In the latter case, the death date will be used as the date of disease progression.

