4.4.2.4 Duration of Response

Duration of response (DoR) is determined separately on disease status using RECIST v1.1 and modified RECIST, both evaluated by the investigator

Duration of response based on RECIST v1.1 assessments:

For overall responders, DoR is defined as the time from the date of first occurrence of a confirmed response (CR or PR) to date of tumor progression or death from any cause or to censoring date:

- end of response coincides with the date of tumor progression or death (in the absence of tumor progression) used for the PFS endpoint
- for a patient without disease progression or death following a response, the censored end of response coincides with the PFS censoring date (that is latest RECIST assessment or start of subsequent cancer therapy whichever occurs first)
- DoR is computed as date of PFS event or censoring minus date of first response + 1.

DoR is not defined for overall non-responders.

Duration of response based on modified RECIST assessments:

For overall responders, DoR is defined as the time from the date of first occurrence of a confirmed response (CR or PR) to date of tumor progression following that confirmed response or death from any cause or to censoring date:

- end of response will be the date of tumor progression after that confirmed response or death (in the absence of tumor progression)
- for a patient without disease progression or death following a response, the censored end of response will be the latest RECIST assessment or start of subsequent cancer therapy whichever occurs first.

DoR is not defined for overall non-responders.

Therefore, in case of disease progression followed by a confirmed response of CR or PR (and no confirmed CR or PR before the disease progression), this confirmed response will be considered as Best overall response and the duration of response will start from this confirmed response until next disease progression or death or censoring.

Additionally, a descriptive KM curve (including estimated median) for DoR is provided based on patients with an overall response.

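### Under the SAP's modified-RECIST rules, confirmed PD with nothing better before it, followed only by SD or an unconfirmed response, counts as disease control; protocol Appendix 2 does not allow this

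*SAP*

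**What the plan says.** **SAP 4.4.2.3 (window).** For RECIST v1.1, the scans used for best overall response (BOR) stop at progression. For modified RECIST, progression is not on the list of end points. The window closes at death, at the last evaluable scan, or at "start of a subsequent anti-cancer therapy". The section adds: "For best overall response based on modified RECIST, all RECIST assessments are considered even after progression". The derivation is otherwise carried over from v1.1.

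**SAP 4.4.2.5 (disease control).** DCR is the sum of the CR, PR and SD rates and is produced under both criteria. After the rules for confirmed CR and PR comes the SD rule: "Otherwise, if there exists at least an assessment of CR, PR or SD, then the patient has Stable disease as Best Overall Response". It sets no condition about earlier PD.

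**SAP 4.4.2.2 (PFS, modified RECIST).** The event for a non-responder is the "date of first occurrence of tumor progression in case the patient is not a responder according to modified RECIST".

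**Protocol Appendix 2.** BOR of SD is defined as: "Criteria for CR, PR, and PD are not met". For patients treated on after confirmed PD: "patients may achieve a best overall response of PR or CR based on tumor regression achieved at any time prior to study treatment discontinuation". SD is not named there.

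**Whether PD needs confirmation.** Protocol 3.3.7 says modified RECIST is used "to allow the apparent increase in tumor burden to be confirmed at a subsequent assessment prior to designation of progressive disease". Appendix 2 says only that PD may be confirmed by a consecutive scan at least 4 weeks later.

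**The concern.** The v1.1 SD rule is safe under v1.1 because the window closes at progression, so any SD it finds came before PD. Carried into a window that stays open after progression, the same rule lets one later SD scan, or one unconfirmed response, replace a confirmed PD. Appendix 2 gives that replacing role to PR and CR only.

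At stake is a protocol-defined secondary endpoint that SAP 4.4.5 repeats across all subgroups. Relative to Appendix 2, the modified-RECIST DCR could be overstated. A reader of the tables would also find the same patient progressed at the first scan in modified-RECIST PFS and disease-controlled in modified-RECIST DCR.

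**Working it through.** No stated figure depends on this rule, so there is nothing in the plan to reproduce. The check applies both sets of rules to the same scans.

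**1. Can such scans exist?** Yes. Protocol 4.6.2 lets the investigator consider continued treatment after confirmed radiographic PD. Protocol Appendix 1 schedules scans until confirmed PD, or until study discontinuation for patients who stay on atezolizumab after pseudo-progression.

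**2. Worked patient** (illustrative sums of diameters; no new lesions, no new therapy). Appendix 2 thresholds: PD is at least 20% and at least 5 mm above the smallest sum on study; PR is at least 30% below baseline. Baseline and nadir are 50 mm.

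| Scan | Sum | Change from nadir | Timepoint response |
|---|---|---|---|
| Week 9 | 62 mm | (62 − 50)/50 = +24%, +12 mm | PD |
| Week 18 | 66 mm | (66 − 50)/50 = +32%, further increase | PD, confirmed |
| Week 27 | 58 mm | (58 − 50)/50 = +16% | SD |

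- SAP BOR, modified RECIST: one SD scan exists, so SD; counted in DCR.
- SAP BOR, RECIST v1.1: window closes at week 9, so PD; not counted.
- Appendix 2 BOR: PD criteria met and confirmed, no PR or CR, so PD; not counted.
- SAP modified-RECIST PFS: event at week 9, 63 + 1 = 64 days; 64/365.25 × 12 = 2.1 months.

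Two controls: PD, PD alone is PD under every rule. PD, PD, PR, PR is PR under both the SAP's modified-RECIST rule and Appendix 2, so the conflict is confined to SD and unconfirmed responses.

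**3. Direction, from all patterns.** Let R be a response, S be SD and P be PD. Take a confirmed response as two consecutive R and confirmed PD as two consecutive P, and let SD before PD count under both rules. With three scans there are 3³ = 27 patterns; with four, 3⁴ = 81.

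| Comparison | 3 scans | 4 scans |
|---|---|---|
| SAP counts disease control, Appendix 2 does not (PD must be confirmed) | 2 (PPS, PPR) | 7 |
| Same, if the first PD already counts | 7 | 21 |
| Appendix 2 counts, SAP does not | 0 | 0 |
| SAP against itself: disease control with a PFS event at scan 1, among patterns starting with P | 7 of 9 | 21 of 27 |

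These are counts of patterns, not of patients. They show direction only: the SAP's rate equals the Appendix 2 rate or exceeds it. In both discrepant three-scan patterns of the first row, nothing better than PD precedes the confirmed PD. That is a necessary condition: with an earlier SD, PR or CR the patient is SD under both rules.

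**4. Scale.** With about 1000 patients, each affected patient adds 100/1000 = 0.1 percentage point. Assuming a DCR of 30, 40 or 50%, the Clopper-Pearson 95% half-width is 2.89, 3.08 or 3.15 points. A shift of one half-width would therefore take about 29 to 32 such patients. The documents do not give the number who would follow this path.

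**The case against.** **The SAP says only that the modified-RECIST derivation is similar to v1.1.** That leaves some room, but no other SD rule is given, and 4.4.2.5 repeats this one for both criteria.

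**Immune-based criteria are meant to credit what happens after PD, and PFS (first event) need not agree with BOR (best status).** For responses this stands. SAP 4.4.2.4 provides for duration of response "in case of disease progression followed by a confirmed response of CR or PR", and nothing here disturbs that. Neither that section nor Appendix 2 extends the credit to SD.

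**The Appendix 2 line on SD is a loose definition.** Read literally over all scans, it would also turn SD followed by PD into PD, widening the three-scan counts to 4 (confirmed PD) and 16 (first PD). This is fair, and it is why the point rests on confirmed PD with nothing better before it, where Appendix 2 separately names PR and CR.

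Three stronger readings are tempting, and the documents do not support them:

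- *Every PD followed by SD is miscounted.* On the 3.3.7 wording, an increase that is not confirmed is not yet PD, so SD could be right for DCR. That case shows only that the SAP's PFS and DCR treat the same scan differently.
- *The exposed group is the 121 of 311 patients treated beyond progression in the earlier cohort (protocol 3.3.8).* In this trial, treatment beyond progression is defined by RECIST v1.1 (4.6.2), under which new or nontarget lesions can mean PD; under modified RECIST, neither alone does. Median treatment beyond progression in that cohort was 7.8 weeks, less than one 9-week scan interval.
- *Appendix 2 ends the response window at treatment discontinuation for everyone.* Its sentence concerns patients treated on after confirmed PD. Protocol 4.5.6 requires scheduled scans to continue after early stopping for reasons such as toxicity, and a general cut-off would discard them.

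**Conclusion.** The conflict is real and narrow. It needs all of the following: PD confirmed under modified RECIST; no SD, PR or CR before it; at least one later evaluable scan before new anti-cancer therapy; and only SD or an unconfirmed response on the later scans. For such a patient the SAP gives disease control, Appendix 2 gives PD, and the SAP's own PFS gives an event at the first PD.

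The bias in modified-RECIST DCR is zero or upward. Its size cannot be derived. It may be small, because scheduled scans generally end at confirmed PD and the patient must be scanned again after that. ORR and DoR are untouched by the SD rule because both need a confirmed response. RECIST v1.1 DCR is untouched provided the 4.4.2.3 window is applied in 4.4.2.5, which does not restate it. The primary endpoint is safety and is not involved. As the study is descriptive with no formal hypothesis, no test or decision depends on this rate. The rule should still be corrected, because as written it departs from the protocol's response criteria without saying so.

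**What to change.** In SAP 4.4.2.3 and 4.4.2.5:

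1. State that, for modified RECIST, SD (or an unconfirmed response counted as SD) must come from scans before confirmed PD, and that after confirmed PD only a confirmed CR or PR can change BOR. If the departure from Appendix 2 is intended, say so and justify it.
2. State whether first or confirmed PD is the modified-RECIST definition. Apply it to BOR and DCR, and either apply it to PFS and DoR as well or explain why they differ.
3. State that the 4.4.2.3 scan windows apply in 4.4.2.5. At most, add whether the Appendix 2 limit of study treatment discontinuation applies to responses reached after confirmed PD.

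The cost is SAP wording and reprogramming; no new data are needed. Modified-RECIST DCR may be equal or slightly lower. If confirmed PD is also used for PFS, some dates will move. A PD-SD-SD patient scanned at weeks 9, 18 and 27 would go from an event at 64 days (2.1 months) to censoring at 189 + 1 = 190 days (190/365.25 × 12 = 6.2 months). That consequence should be weighed when the definition is chosen.
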